Upon review of the first 9 subjects enrolled in the study, the investigators noted that the alternative week regimen may not provide sufficient recovery time in subjects who experience myelosuppressive effects of tipifarnib. Therefore, the protocol was amended (Amendment 2) to adjust the treatment administration schedule to bid on Days 1-7 of 28 day treatment cycles. The investigators considered that by adjusting the dose regimen to allow for a 3 week rest period following each week of dosing, the myelosuppressive effects will be mitigated allowing subjects to make gains on increasing the cell counts as the cycles progress. Additionally, given the prior experience and tolerability with 300 mg bid on Days 1-21 of 28 day treatment cycles, this regimen was incorporated into Amendment 2 to support dose selection in future clinical studies.

[figure not shown]
Both dose regimens are expected to be well tolerated and to potentially provide clinical benefit to subjects with MDS. Furthermore, the current study allows for step-wise 100 - 200 mg dose adjustment based on subject tolerability. The data obtained from this study will be used to select the optimal dose and dose regimen to support the further development of tipifarnib in subjects with MDS

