10.4 Abnormal Laboratory Findings and Other Abnormal Investigational Findings

Abnormal laboratory findings and other abnormal investigational findings (e.g. on an ECG trace) should not be reported as AEs unless they are associated with clinical signs and symptoms, lead to treatment discontinuation or are considered otherwise medically important by the Investigator. If an abnormality fulfills these criteria, the identified medical condition, e.g. anemia, increased alanine aminotransferase (ALT), must be reported as the AE rather than the abnormal value itself.

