12.2.2 Safety and Tolerability

Safety and tolerability of tipifarnib will be assessed based on the following:

- Incidence, duration, and severity of TEAEs, SAEs, AEs resulting in permanent discontinuation of study drug, and deaths within approximately 30 days from the last dose of study drug (or immediately before the administration of another anticancer treatment)
- Changes in laboratory test results

AEs will be coded using the latest available version of the Medical Dictionary for Regulatory Activities (MedDRA). TEAEs are defined as AEs that start on or after the first dose of study

drug and within approximately 30 days of the last administration of study drug. AEs will be summarized by the number and percentage of subjects who experienced the event, according to system organ class and preferred term. A subject reporting multiple cases of the same AE will be counted once within each system organ class and similarly counted once within each preferred term

Unless specified otherwise, the denominator for these calculations will be based on the number of subjects in each cohort who received at least one administration of tipifarnib, irrespective of the total number of doses or treatment cycles administered. These conventions will be appropriately modified to calculate AE incidence rates separately for each cycle that study therapy is administered. AE incidence rates may also be calculated based on other measures of subject exposure (e.g., total number of treatment cycles administered). AEs will also be summarized by NCI CTCAE v.4.03 severity grade, by relationship to each study drug and by treatment regimen. Additional summaries may also be provided for SAEs, and events resulting in the permanent discontinuation of therapy. All AEs will be included in individual subject listings.

The incidence of grade 3 and 4 hematological toxicities (including neutropenia, thrombocytopenia, and anemia) will be provided by treatment cycle and across all treatment cycles. The toxicity grades for laboratory tests will be based on NCI CTCAE v.4.03 criteria. The use of blood transfusions (platelets, red blood cells, whole blood) and/or growth factor support will be reported.

Vital sign results (heart rate, blood pressure and temperature) will be summarized descriptively for each scheduled and unscheduled protocol time point. Changes will be calculated relative to the assessments at baseline.

Sample Size Determination

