4. STUDY DESIGN

4.1. General Study Design and Plan

This phase 2 study will investigate the antitumor activity in terms of ORR of tipifarnib in approximately 36 eligible subjects with MDS who have no known curative treatment. Eligible subjects may have received no more than 2 prior systemic regimens. Prior systemic regimens are those that are considered standard of care for the treatment of MDS, have been received at standard doses for at least one full treatment cycle and exclude erythropoiesis-stimulating agents (ESA).

A two-stage study design will be employed in order to minimize the number of study subjects treated if tipifarnib were considered not sufficiently efficacious to grant further development in this subject population. This design is intended to allow the termination of accrual in case of unacceptably low efficacy as measured by ORR.

In the first stage, 22 eligible subjects will be enrolled and randomized to 1 of 2 dosing regimens (regimen 1 or regimen 2). If two or more responses are observed in a given dose regimen cohort, 7 additional study subjects will be enrolled.

Subjects will be randomized to receive tipifarnib orally with food, twice a day (bid) according to one of the following dose regimens:

- **Regimen 1: 600 mg bid for 7 days on Days 1-7 in 28 day cycles** (i.e. 1 week on / 3 weeks off).

At the discretion of the investigator, the dose of tipifarnib may be increased to 800 mg bid if the subject has not experienced dose limiting toxicities at the 600 mg dose level. Subjects are not to be dose escalated until after completing Cycle 1 to ensure the dosing regimen is tolerated prior to escalation. Stepwise 200 mg dose reductions to control treatment-related, treatment-emergent toxicities are also allowed. Subjects who develop serious adverse events (SAE), \geq grade 2 treatment-emergent adverse events (TEAE) that are deemed related to tipifarnib and lasting \geq 14 days will not undergo dose escalation.

- **Regimen 2: 300 mg bid for 21 days on Days 1-21 in 28 day cycles** (i.e. 3 weeks on / 1 week off).

Stepwise 100 mg dose reductions to control treatment-related, treatment-emergent toxicities are allowed.

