10.1. Adverse Events

Adverse events will be coded using the latest available version of the Medical Dictionary for Regulatory Activities (MedDRA). Treatment-emergent adverse events are defined as AEs that start on or after the first dose of study drug and within approximately 30 days of the last administration of study drug. AEs will be summarized by the number and percentage of subjects who experienced the event, according to SOC and PT. A subject reporting multiple cases of the same AE will be counted once within each SOC and similarly counted once within each PT. For summaries by maximum severity, each subject will be counted only once under the most severe event.

Unless specified otherwise, the denominator for these calculations will be based on the number of subjects who received at least one administration of tipifarnib regardless of the total number of doses or treatment cycles administered. These conventions will be appropriately modified to calculate AE incidence rates separately for each cycle that study therapy is administered. AE incidence rates may also be calculated based on other measures of subject exposure (e.g., total number of treatment cycles administered). For subjects enrolled prior to Protocol Amendment 3, their AE counts will only be provided in the Total column (Regimen 1 + Regimen 2 + Original Cohort). Regimen 1 and Regimen 2 subjects will be presented separately and in the Total columns.

AE durations will be calculated using all TEAEs. For any AE that is still ongoing at the end of study, we will use the last contact date as the end of AE stop date for calculation the duration of AEs. Median, minimum and maximum of AE durations will be reported.

AEs will also be summarized by NCI-CTCAE version 4.03 severity grade and by relationship to each study drug. Additional summaries may also be provided for SAEs, and events resulting in the permanent discontinuation of therapy. All AEs will be included in individual subject listings.

Hematologic abnormalities reported as AEs that were coded to preferred terms in the Investigations SOC have been pooled with appropriate terms in the Blood and Lymphatic System SOC for tabulation for the following categories:

- Platelet count decreased = Thrombocytopenia;
- Neutrophil count decreased = Neutropenia;
- White blood cell count decreased = Leukopenia;
- Lymphocyte count decreased = Lymphopenia.

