10.2. Clinical Laboratory Evaluations

Hematological toxicities Grade 3 or above based on NCI-CTCAE version 4.03 criteria will be summarized across all treatment cycles. A shift table will be presented for the shift from baseline to worst post-baseline severity grade. Severity grading is based on the National Cancer Institute Common Terminology Criteria for Adverse Events (CTCAE), version 4.03, with normal ranges defined from the American Medical Association Standard Lab Normal Ranges. For laboratory values that fall outside the defined severity ranges, a value of 0 was entered. Not Applicable is given to those laboratory values that have no associated CTCAE severity criteria.

The data for clinical laboratory evaluations (including hematology, chemistry, coagulation, and pregnancy testing) will be presented in listings. In addition to the results, these listings will present the normal range, toxicity grade, and clinical assessment (Normal; Abnormal, but not clinically significant; Abnormal, clinically significant) associated with evaluations.

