15. CHANGES IN THE STATISTICAL METHODS FROM THOSE STATED IN THE PROTOCOL

None.

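### SAP 10.2 omits the by-cycle summary of grade 3 and 4 hematological toxicity that Protocol 12.2.2 requires, and SAP 15 declares no change

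*SAP*

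**What the plan says.** Protocol 12.2.2 states that the incidence of grade 3 and 4 hematological toxicities, naming neutropenia, thrombocytopenia and anemia, "will be provided by treatment cycle and across all treatment cycles". Its next sentence bases the grading of laboratory tests on CTCAE v4.03.

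SAP 10.2 says: "Hematological toxicities Grade 3 or above based on NCI-CTCAE version 4.03 criteria will be summarized across all treatment cycles". It also says: "A shift table will be presented for the shift from baseline to worst post-baseline severity grade". The remaining laboratory output in that section is listings, which carry toxicity grades.

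SAP 15, headed "CHANGES IN THE STATISTICAL METHODS FROM THOSE STATED IN THE PROTOCOL", has the single entry that there are none.

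SAP 10.1 has a by-cycle provision, but for adverse events: the conventions are to be adapted to "calculate AE incidence rates separately for each cycle that study therapy is administered". The same section plans an overview of AE incidence adjusted for exposure, as mean events per treatment cycle with 95% confidence intervals. It also plans tables of hematology-related treatment-emergent AEs by maximum grade.

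**The concern.** A summary that the protocol promises has gone from the SAP, and the section meant to record such changes says that nothing changed. A reader of the study report would not know that the by-cycle table had been planned.

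The table bears on a question that the trial asks. Protocol 9.4 explains that Amendment 2 gave Regimen 1 a three-week rest to lessen myelosuppression, "allowing subjects to make gains on increasing the cell counts as the cycles progress", and that the results will guide the choice of dose and regimen. Whether severe cytopenia comes early and eases, or builds up, is a question about time. An incidence over all cycles and a worst-grade shift count each subject at the worst point reached, so neither shows when that point fell.

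**Working it through.** No formula in the plan is at issue. The check sets the sections side by side, then works out what the restored table could show.

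**1. Required against planned**

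| Laboratory summary of severe hematological toxicity | Protocol 12.2.2 | SAP 10.2 |
|---|---|---|
| By treatment cycle | required | absent |
| Over all cycles | required | present |
| Shift from baseline to worst grade | not mentioned | present |
| Departure declared in SAP 15 | n/a | none |

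The SAP names 1 of the 2 required summaries. It names 2 laboratory tables in all, and 0 are by cycle. The general convention in SAP 13 groups results by stage and cohort, so it does not supply the missing split.

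**2. Does SAP 10.1 fill the gap?** Not fully.
- Protocol 12.2.2 contains the by-cycle AE convention and, separately, the by-cycle hematological summary. The protocol therefore does not treat the first as a substitute for the second. The SAP carried over the first and shortened the second.
- Under Protocol 10.4, abnormal laboratory findings "should not be reported as AEs unless they are associated with clinical signs and symptoms, lead to treatment discontinuation" or are judged medically important by the investigator. An isolated low count can be graded in the laboratory data without ever becoming an AE.
- None of the summary tables that SAP 10.1 goes on to name, including the hematology-related ones, is specified by cycle. The exposure-adjusted rate belongs to the AE overview, not to graded laboratory values.

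**3. What scheduled counts would feed a by-cycle table?** Hematology is scheduled on Day 1 of every cycle, and on Day 22 (± 5 days) in Cycles 3, 6, 9, 12 and every third cycle after that (Protocol Table 1; SAP 4.6). The Cycle 1 Day 1 count is pre-dose (Protocol 11.2). I assume that later Day 1 counts are also pre-dose and that cycles are not delayed, so the next Day 1 is Day 29.
- Post-dose scheduled counts per cycle: 1 in Cycles 1, 2, 4 and 5; 2 in Cycles 3, 6 and 9.
- Days from last dose to the next Day 1: Regimen 1, 29 − 7 = 22; Regimen 2, 29 − 21 = 8. With the ± 2 day window these are 20 to 24 and 6 to 10, or about 3 weeks against about 1 week.
- Days from last dose to a Day 22 visit held on time: Regimen 1, 22 − 7 = 15; Regimen 2, 22 − 21 = 1.

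Regimen 1 therefore always has 14 more drug-free days before the same visit. Cycles with two counts also have more chance of recording a severe grade than cycles with one.

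**4. Baseline grade.** Inclusion criterion 7a requires a neutrophil count below 1000/mm³. The documents do not print the CTCAE cut-offs. If grade 3 neutropenia is assumed to begin just below 1000/mm³, every subject who still meets 7a at baseline starts at grade 3 or worse. If the cut-off is lower, only some do. In either case a crude by-cycle incidence of neutropenia partly reflects the entry criterion.

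**The case against.** The strongest reply accepts the mismatch and disputes its weight.

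- **Information is available elsewhere.** SAP 10.1 offers by-cycle and exposure-adjusted AE rates and pools laboratory-coded cytopenias with the matching AE terms. The listings carry grades, so by-cycle counts could be rebuilt by hand. Gains in counts are also assessed through hematologic improvement within the response rate, the hemoglobin rise in transfusion independence, and the summary of transfusion and growth factor use. This stands as mitigation. None of it is the laboratory summary that the protocol names.
- **The table would be hard to read.** Most subjects may enter with severe neutropenia, the counts fall at different drug-free intervals in the two regimens, and later cycles hold few subjects, only those still on treatment. This stands in full. It governs how the table should be built, and a sponsor could give it as a reason for dropping the table. SAP 15 gives no reason.
- **The shells may contain it.** SAP 14 leaves layout to a companion document that was not available. This stands as a limit on the finding, but SAP 10.2 and SAP 15 would still need to agree with the protocol.

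A reader might also infer that the by-cycle table is needed to isolate the effect of 800 mg bid, since "Subjects are not to be dose escalated until after completing Cycle 1". The documents do not support that. Neither links the table to escalation. Escalation is discretionary, so Regimen 1 cycles from Cycle 2 on may mix 800, 600, 400 and 200 mg bid. The table separates time, not dose.

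**Conclusion.** The point holds as an undeclared inconsistency between protocol and SAP: one of two required summaries of severe hematological toxicity is missing from SAP 10.2, and SAP 15 says that nothing changed. It is worth correcting because the schedule of Regimen 1 was chosen with recovery over cycles in mind, and the data are to inform regimen selection.

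Its reach is limited. The primary endpoint, the stage decision and the sample size do not depend on it. A reader might infer that the omission biases the regimen comparison by a known amount. The documents give no per-cycle toxicity risk and no expected number of cycles by regimen, so no such amount can be stated. Nor can one infer that the SAP has no by-cycle safety information, given SAP 10.1.

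The conclusion rests on the SAP text alone, without the table shells. The caution about neutrophil grade rests on an assumed CTCAE cut-off, and the visit-timing figures assume undelayed cycles and pre-dose Day 1 counts.

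**What to change.** In SAP 10.2, restore the by-cycle summary beside the one over all cycles:

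- Show grade 3 and 4 neutropenia, thrombocytopenia and anemia by regimen and by cycle.
- Use as denominator the subjects who started the cycle and have a post-dose count for it. State the rule that assigns each count to a cycle, including the pre-dose Day 1 count of the next cycle.
- Add worsening from baseline grade by cycle, with baseline as already defined in SAP 13.
- Base the main table on scheduled counts. Show unscheduled counts separately, because under Protocol 11.3 they are taken when clinically indicated and so come more often from sicker subjects. A separate summary of them needs a stated exception to SAP 13.
- Add a note that Day 22 counts exist only in every third cycle, that the next Day 1 count falls about 3 weeks after the last dose in Regimen 1 but about 1 week after it in Regimen 2, and that later cycles hold few subjects, all still on treatment. Label the table descriptive, not a clean comparison of regimens.

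If the sponsor does not want the table, SAP 15 should declare its removal and give the reason.

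The cost is a paragraph and a by-cycle table with its baseline-worsening display, or one line in SAP 15. Hematology results and dosing dates are already collected, so no new assessment is needed.

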Subjects who terminate treatment for reasons other than death or disease progression will be assessed at regular intervals for disease progression (approximately every 12 weeks) and leukemic transformation (monthly blood counts). Disease assessments performed during the first 9 months from the start of the subject's participation in the study will include bone marrow evaluation. Thereafter, bone marrow evaluations will occur during disease assessments in accordance with institutional standard practice. These assessments will continue until disease progression, withdrawal of subject's consent to study procedures or initiation of another anticancer therapy.

All subjects will be followed-up for safety during treatment and up to approximately 30 days (30 ± 7 days) after treatment discontinuation or until immediately before the initiation of another anticancer therapy, whichever occurs first. Additional follow up may be implemented until the subject recovers from any emergent treatment related toxicity or the adverse event is considered

irreversible by the Investigator. Target organ toxicities will be monitored via clinical and laboratory assessments using the NCI CTCAE v. 4.03 criteria.

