7. At the screening visit, record the number of RBC, whole blood and platelet transfusions for the four months prior to Cycle 1 Day 1; for all other visits, the number of transfusions should be recorded since the last study visit.
8. Assessed from date of first signature of ICF, throughout the course of treatment and approximately 30 days after treatment discontinuation. Additional assessments may be performed until AE resolution or the AE is deemed irreversible by the Investigator.
9. Assessment is to be performed within 14 days prior to the first administration of study drug.
10. If not collected within the 14 days prior to Cycle 1 Day 1, record subject's weight and vital signs prior to dosing on Cycle 1 Day 1 only.
11. Assessment is to be performed within 72 hours prior to first administration of study drug on Day 1 of Cycle 1.
12. To be performed in women with childbearing potential only
13. Assessment is to be performed beginning on Cycle 2 Day 1 and Day 1 of every cycle thereafter.
14. Fasting for laboratory testing is not required. Laboratory tests may be conducted on additional time points if deemed necessary by the Investigator. Samples will be analyzed locally at the clinical site or its reference laboratory. Laboratory assessments may be repeated if values are borderline to inclusion level or may change due to best supportive care measures. Hematology should include: hemoglobin, reticulocytes, platelets, WBCs, neutrophils, neutrophil precursors (promyelocytes, myelocytes, metamyelocytes, band neutrophils), monocytes, lymphocytes and blasts. Serum chemistry should include: AST, ALT, total bilirubin, creatinine, BUN, potassium and calcium. Coagulation should include: PT/INR, APTT.
15. Screening hematology tests must be performed \geq 1 week prior to Cycle 1 Day 1. Additionally, hematology tests must be repeated prior to dosing on Cycle 1 Day 1.
16. Serum chemistry tests do not need to be repeated on Cycle 1 Day 1 if the screening tests were conducted within 72 hours prior to the first dose of tipifarnib.
17. Required only for subjects who terminated treatment for reasons other than death or disease progression and assessments should be performed monthly.
18. Investigator review of subject RBC transfusions, hematology and bone marrow evaluation (if available) for completion of response assessment.
19. Protocols will be provided in a separate lab manual for sample collection, processing and shipment.

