10. SAFETY ANALYSES

Safety and tolerability of tipifarnib will be assessed based on the following:

- Incidence, duration and severity of TEAEs, SAEs, AEs resulting in permanent discontinuation of study drug, and deaths within approximately 30 days from the last dose of study drug (or immediately before the administration of another anti-cancer treatment)
- Changes in laboratory test results
- Serum Chemistry: Blood Urea Nitrogen, Creatinine, Potassium, Calcium, Total Bilirubin, ALT, AST
- Hematology: White Blood Cell Count, Hemoglobin, Platelet Count, Absolute Neutrophil Count, Neutrophil Precursors (promyelocytes, myelocytes, metamyelocytes, band neutrophils), Lymphocytes, Monocytes, Blasts, and Reticulocytes.
- Coagulation panel: PT/INR, APTT
- Changes in vital signs: blood pressure, heart rate, temperature

Unless explicitly indicated otherwise, all analyses for safety will be based on the ASaT population.

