13. DATA HANDLING CONVENTIONS

Analyses will be performed using SAS® [SAS Institute 2011] Version 9.3 or higher.

The clinical database will be locked prior to the initiation of the Stage 1 statistical analyses. A database lock is defined as a stable database that can be analyzed and reported. Changes to a locked database must be authorized in writing by the study sponsor [REDACTED]

The data conventions include the following.

- Data will be described and summarized by study stage (Stage 1 or Stage 2), Stage 1 cohort (starting dose level and schedule), or Stage 2 cohort (disease type).
- Summary tables for continuous variables will contain the following statistics: N (number of subjects in the population); n (number of subjects with data for that variable); mean; standard deviation; median; minimum; and maximum. Selected statistics may also include 2 sided 95% normal approximation confidence intervals (CI) on the mean.
- Summary tables for categorical variables will include: N (number of subjects in the denominator); n (number of subjects in the numerator); and percent. Selected statistics also may include 2-sided 95% CIs for the percent, calculated using the CL=AGRESTICOULL option in SAS PROC FREQ.

- The baseline value for a given parameter is the last value prior to the first dose. A value is considered to be post-baseline if it is obtained after the first dose. A value is considered to be postdose on a given cycle day if it is obtained after the dose is administered on that day.
- Data from all study centers will be pooled for all analyses.
- Unless otherwise specified, statistical testing will be 2-sided at a nominal 0.05 level of significance.
- Study day is defined as calendar date – date of first treatment + 1 if the calendar date is on or after the date of first treatment, and calendar date – date of first treatment if the calendar date is before the date of first treatment
- Measurements from unscheduled visits will be included in listings, but not summary tables.
- Missing data conventions for individual endpoints are described in the SAP section for the endpoint.
- Additional exploratory analyses may be performed as deemed appropriate after review of the pre-specified analyses. Log-transformations or nonparametric tests may be applied to measurements displaying a significant degree of non-normality.
- Listings will be provided for all data collected in the eCRF.

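### The laboratory shift table has no end date, so scheduled hematology drawn months after the last dose can set a subject's worst grade in a safety table

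*SAP*

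**What the plan says.** SAP 10.2 plans two laboratory summaries: hematological toxicities of Grade 3 or above, taken across treatment cycles, and a shift table. For the latter: "A shift table will be presented for the shift from baseline to worst post-baseline severity grade". No period is given there. The general rule in SAP 13 is "A value is considered to be post-baseline if it is obtained after the first dose". It has no upper limit, and the only values it keeps out of summary tables are those from unscheduled visits.

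Hematology continues after treatment for some subjects. Note 17 to the schedule in SAP 4.6 reads "Required only for subjects who terminated treatment for reasons other than death or disease progression and assessments should be performed monthly", and Protocol 11.6.1 lists the same monthly test. SAP 4.1 gives leukemic transformation as the reason for the monthly counts, and on their duration says "These assessments will continue until disease progression, withdrawal of subject's consent to study procedures or initiation of another anticancer therapy".

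The other safety windows are closed. SAP 10.1 defines treatment-emergent events as those that "start on or after the first dose of study drug and within approximately 30 days of the last administration of study drug". SAP 4.1 says "All subjects will be followed-up for safety during treatment and up to approximately 30 days" after discontinuation, or until just before another anticancer therapy. In the list of safety measures in SAP 10, deaths carry the 30-day limit, but the laboratory item, "Changes in laboratory test results", carries none.

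**The concern.** The shift table sits among the safety analyses and is graded by toxicity criteria, so a reader will take it as a picture of what happened to blood counts under tipifarnib. Under the stated rule, a fall in platelets or hemoglobin months after the last dose, in a disease that itself lowers counts, can become the subject's worst grade. Nothing in the table would separate it from a fall during treatment.

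The hematology-related adverse event tables by maximum grade (SAP 10.1) stop at about 30 days. The two displays would then cover different periods for the same cytopenias and could disagree for that reason alone.

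This matters because Protocol 9.4 gives myelosuppression as the reason for moving to the 1-week-on, 3-weeks-off schedule and says the data will be used to choose a regimen. The cohorts are small. If a cohort holds 11 or 18 treated subjects, one reclassified subject moves a percentage by 1/11 = 9.1 or 1/18 = 5.6 points.

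**Working it through.** The plan gives no figure on this point to reproduce. The check is a trace of definitions, followed by a count of visits.

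**Does any rule close the window?**
- SAP 10.2: worst post-baseline grade, no end.
- SAP 13: post-baseline starts after the first dose, no end.
- SAP 13, unscheduled visits: does not apply, because the monthly counts are scheduled.
- SAP 10.1: the 30-day limit applies to adverse events only.
- Protocol 12.2.2: lists laboratory changes without a window and does not mention a shift table.

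No rule in either document closes it.

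**Which rows are affected?** In the schedule (SAP 4.6), hematology is the only safety laboratory panel in the follow-up column. Chemistry and coagulation end with the End of Treatment visit. The Grade 3 or above summary is already worded by treatment cycle.

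**How many late counts can there be?** Inputs are 28-day cycles, last dosing day 7 (Regimen 1) or 21 (Regimen 2), hematology on Day 1 of each cycle from Cycle 2 and on Day 22 of Cycles 3, 6 and 9. Three assumptions are added: End of Treatment visit at last dose + 30 days; follow-up every 30 days; follow-up to Day 365 without progression, consent withdrawal or new therapy. Day 365 approximates the last-enrolled subject's time to the end of study in SAP 4.4.

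With last dose on day L, late counts = whole part of (365 − L − 30)/30.

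- Stop after Cycle 2: L = 35 or 49. Late counts: 300/30 gives 10, 286/30 gives 9. Counts up to L + 30: 2 (Cycle 2 Day 1, End of Treatment).
- After Cycle 3: L = 63 or 77. Late: 9 or 8. Up to L + 30: 4.
- After Cycle 6: L = 147 or 161. Late: 6 or 5. Up to L + 30: 8.
- After Cycle 9: L = 231 or 245. Late: 3 or 3. Up to L + 30: 12.

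**How often would a late count set the worst grade?** The documents give no rate. As an assumption, let each late count have an independent chance p of being worse than any grade seen inside the window. The chance over n counts is 1 − (1 − p)^n:

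- p = 1%: 8.6% (n = 9) to 9.6% (n = 10)
- p = 3%: 24.0% to 26.3%
- p = 5%: 37.0% to 40.1%

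These show a range for one unfavorable pattern of follow-up. They are not estimates for the trial.

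**Does it favor one regimen?** A subject still on treatment at Day 365 has Day 1 of Cycles 2 to 14 (13 counts) plus Day 22 of Cycles 3, 6, 9 and 12 (4 counts), 17 in all. The subject who stopped after Cycle 2 has 2 + 9 or 10 = 11 or 12. If disease alone gave a 3% chance of a worse grade at every count in everyone, the open window would give 28% to 31% for the early stopper and 40% for the subject still on treatment. With the window closed at 30 days, the early stopper's figure is 1 − 0.97² = 6%.

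**The case against.** The strongest reply is that the table does what its label says. The SAP writes post-baseline. A reader might infer that late counts are scored as on-treatment toxicity, but the SAP never uses that term. Using all values after baseline can also be defended: SAP 4.1 allows follow-up beyond 30 days until related toxicity recovers, and an open window would catch late or persistent cytopenia. The label point stands. It does not answer the mixing of leukemia-surveillance counts with safety counts in one undivided cell.

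A reader might also infer that a regimen with more early stops would look more toxic for that reason alone. The documents do not support that. Subjects who stay on treatment have more scheduled counts in a year (17 against 11 or 12), so disease-driven worst grades arise there too. Closing the window makes observation time less equal. The direction of any regimen difference is open.

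A 30-day intent for laboratory data is an inference from the adverse event and safety follow-up windows; no text states it. Myelosuppression within 30 days is also reported elsewhere, in the hematology-related event tables, and all laboratory values are listed with grades. The shift table is one descriptive display with no test or decision attached. Finally, SAP 14 leaves layout to a companion document of table shells that is not available here and may set a period. These points limit the size of the problem. They do not remove the rule as written in the SAP.

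**Conclusion.** The point holds within these limits. By the SAP's own definitions, scheduled hematology drawn long after the last dose can fix a subject's worst grade in the shift table, and no stated rule prevents it. It can happen only in subjects who stop without progression or death, and only until progression, consent withdrawal or another anticancer therapy.

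The conclusion rests on the wording and needs no assumed rate. The counts of 3 to 10 late samples rest on the visit pattern and Day 365 horizon set out above; the percentages rest on invented values of p. The documents do not show how many of the approximately 36 subjects would be affected. Sample size, error rates and the stage decision are unaffected. It is a safety-reporting defect worth correcting before the tables are run.

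**What to change.** In SAP 10.2, state that the shift table's worst post-baseline grade uses values from the first dose to about 30 days after the last dose, or to the start of another anticancer therapy if earlier. Word the limit so that the End of Treatment sample is kept: that visit is allowed at 30 ± 7 days, and a cut at exactly 30 days would drop samples taken on days 31 to 37. Show later follow-up counts in a separate display or in listings. Carry the same period into the table shells.

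Leave the general post-baseline definition in SAP 13 alone, since it serves every parameter. The Grade 3 or above summary needs no change.

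The cost is one sentence and a date filter, with no new data. There is a small price: cytopenia that appears or persists after the window is seen only in the separate display, and subjects who stop early contribute fewer counts to the table. A footnote giving the window would make both plain.
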